## 7.4 Duration of study drug administration and treatment compliance

For the FAS and safety analysis set, descriptive statistics of the compliance rate of the study drug (no calculation of 95% CI of the mean) should be calculated to provide the number and proportion of subjects with a compliance rate of  $\geq 80\%$  and  $< 80\%$ .

For the FAS and the safety analysis set, the descriptive statistics of the duration of study drug administration should be calculated (no calculation of 95% CI of the mean).

For the FAS and safety analysis set, the descriptive statistics of the cumulative dosage of the study drug (no calculation of 95% CI of the mean) should be calculated.

## 7.5 Efficacy analysis

As a general rule, efficacy analysis will be performed on the FAS. When necessary, descriptive statistics for continuous variables should be calculated and frequency and proportion will be calculated for discrete variables. No data from the day after the rescue therapy implementation date should be included in the efficacy analysis.

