8.5.3 Rescue therapy

The following rescue therapy options will be provided as needed for subject safety. Even if rescue therapies are performed, the subject can continue in the study unless investigators/subinvestigators determine study withdrawal is appropriate. Details of any rescue therapy implemented will be recorded in the subject's CRF.

(1) ESA formulations

If a subject has received maximum dosages of MT-6548 Tablets for ≥ 2 weeks and meets all criteria below, the investigator/subinvestigator may administer an ESA as a rescue therapy to improve Hb levels if necessary in order to secure subject safety. An ESA-based rescue therapy may also be provided without meeting the criteria below if the investigator/subinvestigator considers it necessary to secure subject safety, such as in cases of acute decreases in Hb levels. Administration of MT-6548 Tablets will be discontinued when an ESA-based rescue therapy is provided. Administration of MT-6548 Tablets may be resumed after an improvement in Hb levels and should not be coadministered with a rescue therapy with an ESA. Subjects who are not expected to resume administration of MT-6548 Tablets will be withdrawn from the study.

- ✓ Anaemia or anaemia symptoms (e.g., fatigue, weakness, shortness of breath, chest pain, confusion, dizziness) become aggravated compared to the first day of the treatment period to the point they are clinically problematic.
- ✓ Hb levels drop to < 8.0 g/dL.

(2) RBC transfusion

Usually, RBC transfusions are performed when clinically necessary in instances of acute or major bleeding. For less severe anemia, which may be exacerbated, or moderate to severe anemia symptoms, RBC transfusions may be performed as needed clinically at the discretion of the investigator/subinvestigator.

(3) Phlebotomy

Phlebotomy may be performed at investigator/subinvestigator discretion in cases of hyperviscosity syndrome, if the rate of Hb increase is concerning to investigators/subinvestigators, or if Hb levels are high enough to warrant concern to investigators/subinvestigators.

Rationale

Set out of consideration for subject safety.

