13.2 Data handling

(1) Definition of missing values

If test measurements are missing or if problems with samples etc. result in invalid measurements or reference values, these are handled as missing values.

(2) Handling of timepoint data for statistical summaries at each measurement timepoint

Statistical summaries for each evaluation timepoint will use data compliant with permitted ranges as described in “Table 9.1-1 Permitted ranges for study center visits.” There will be no supplementing with data from outside the permitted range.

If multiple data points exist within the permitted range, then the one closest to the scheduled day will be used. If there are deviations from the scheduled day, then data points prior to the scheduled day will be used for efficacy evaluation, and data points after the scheduled day will be used for safety evaluation.

(3) Handling of efficacy endpoints if rescue therapy was implemented

No data obtained after implementation of rescue therapy will be used for efficacy evaluation.

(4) Imputation of missing values

Missing values for treatment period Week 24 will be imputed by last observation carried forward (LOCF). Data from treatment period Week 24 with missing values imputed will be used as data from the completion of treatment period.

Required regulations for data handling other than those enumerated above will be described in the statistical analysis protocol prior to data lock.

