#### 3.1.2 Other endpoints

- (1) Changes in mean Hb values from the first day of the treatment period at Week 20 and Week 24 of the treatment period
- (2) Proportion of subjects with a  $\geq 1.0$  g/dL increase from baseline in mean Hb values at each time point in the treatment period
- (3) Proportion of subjects receiving rescue therapy with ESA formulations, red blood cell transfusion, or phlebotomy
- (4) Study drug dosage
- (5) Total number of study drug dosage adjustments
- (6) Iron supplement dosage
- (7) Proportion of subjects receiving iron supplements via oral, intravenous, or any route.

- (8) Proportion of subjects with serum ferritin  $\geq 100$  ng/mL or TSAT  $\geq 20\%$
- (9) Changes and rate of changes in iron-related indices (serum iron, TIBC, TSAT, and serum ferritin levels) and hepcidin from the first day of the treatment period
- (10) Changes in hematocrit, red blood cell count, reticulocytes (count and rate), mean corpuscular volume, mean corpuscular hemoglobin, and erythropoietin from the first day of the treatment period
- (11) Changes and rate of changes in systolic blood pressure, diastolic blood pressure, lipids (total cholesterol, LDL-C, HDL-C, LDL-C/HDL-C ratio, triglycerides), and blood glucose from the first day of the treatment period
- (12) QOL indices (EQ-5D-5L, KDQOL)

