### **6.3 Handling of efficacy endpoints if rescue therapy is performed**

If rescue therapy is performed, data from the day after rescue therapy should not be used to assess efficacy.

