#### **7.6.8 Proportion of subjects with documented Hb values of $\geq 12.0$ g/dL or $\geq 13.0$ g/dL**

The number and proportion of subjects with confirmed Hb values  $\geq 12.0$  g/dL or  $\geq 13.0$  g/dL, after the first day of the treatment period, in each period between scheduled study visits and during the entire treatment period from the first day to Week 24 of the treatment period should be provided. If Hb value is  $> 12.0$  g/dL or  $13.0$  g/dL in the same subject, the subject should be counted as 1 in both categories.

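### The post-rescue data exclusion exempts no endpoint, so it conflicts with the Week 24 windows set for the rescue, study drug dose, dose-adjustment and iron endpoints

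*SAP*

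**What the plan says.** **The exclusion.** SAP 7.5: "No data from the day after the rescue therapy implementation date should be included in the efficacy analysis". SAP 6.3: "data from the day after rescue therapy should not be used to assess efficacy". Protocol 13.2(3): "No data obtained after implementation of rescue therapy will be used for efficacy evaluation". No endpoint and no type of rescue is exempted. Under the SAP the rescue day itself stays in.

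**The endpoints it reaches.** SAP 3.1.2, under efficacy endpoints, lists at (3) "Proportion of subjects receiving rescue therapy with ESA formulations, red blood cell transfusion, or phlebotomy", at (4) study drug dosage, at (5) "Total number of study drug dosage adjustments", at (6) "Iron supplement dosage" and at (7) the proportion receiving iron by route. All are analysed in 7.5.2(3) to (7), inside the section that the exclusion governs.

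**The windows of those endpoints.** SAP 7.5.2(3), (6) and (7) ask for results in each visit interval and over the whole treatment period to Week 24. 7.5.2(5) does the same for dose adjustments and counts an interruption as one. 7.5.2(4) runs mean daily dose up to Week 24. Protocol 10.1.2(3) to (7) also runs to Week 24. None of these stops at rescue.

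**What can happen after rescue.** Under protocol 8.5.3 a rescued subject may remain in the study. For an ESA rescue: "Administration of MT-6548 Tablets will be discontinued when an ESA-based rescue therapy is provided". Study drug may be resumed later.

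**The concern.** Removing post-rescue data is sensible for Hb and other measurements that a rescue may distort. It does not suit endpoints that record what treatment was given. A transfusion after an ESA rescue is an event that the transfusion endpoint exists to count, and the time off study drug after an ESA rescue is part of the dosing record.

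Two instructions in the same SAP section therefore point in opposite directions for the same subject, and the programmer has to choose. The literal choice can only lower the rescue and interruption counts. It also removes post-rescue dosing and iron from tables labelled as full analysis set, including the Week 20 to 24 dose summaries by site (7.5.5) and by subgroup (7.5.6).

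**Working it through.** There is no planned figure to reproduce. The sample size of 20 was set on feasibility (protocol 6.1), and the documents give no rescue rate. The check is textual, followed by illustrations whose rescue counts and dose levels are assumptions.

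**1. Does anything in the documents resolve the conflict?** No. The errata touch 7.5.2(5) only to delete one by-interval tabulation, and they leave 6.3 and 7.5 alone. SAP section 9 declares only the addition of mean corpuscular volume and mean corpuscular hemoglobin.

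**2. What does the literal reading remove?**

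| Event after a first rescue | Whole-period result | By-interval result |
|---|---|---|
| Rescue of a different type | lost | lost |
| Further rescue of the same type | unchanged, because subjects are counted once | lost in the later interval |
| Interruption dated on the rescue day | kept | kept |
| Interruption dated the next day or later | lost | lost |
| 0 mg days, resumed doses, dose changes, iron after the rescue day | lost | lost in later intervals |

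**3. Rescue proportions.** The exact (Clopper-Pearson) limits for x of n are the 2.5% quantile of Beta(x, n − x + 1) and the 97.5% quantile of Beta(x + 1, n − x). The lower limit is 0 when x = 0. With n = 20:

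- 0/20 = 0%: upper limit 1 − 0.025^(1/20) = 16.8%, so 0 to 16.8%.
- 1/20 = 5.0%: 0.1 to 24.9%.
- 2/20 = 10.0%: 1.2 to 31.7%.

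Suppose one subject has an ESA rescue on Day 60 and a transfusion on Day 100, and nobody else is transfused. All data give 1/20 and the exclusion gives 0/20. If another subject is transfused without any earlier rescue, the figures are 2/20 and 1/20. Each lost subject is 1/20 = 5 percentage points.

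**4. Mean daily dose in an interval wholly after an ESA rescue.** Assume k of 20 subjects are at 0 mg throughout and the others at dose m. With all data the mean is m × (20 − k)/20. With the exclusion it is m, on 20 − k subjects. For m = 450 mg:

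| k | Exclusion | All data (n = 20) |
|---|---|---|
| 1 | 450 mg (n = 19) | 427.5 mg |
| 2 | 450 mg (n = 18) | 405 mg |
| 3 | 450 mg (n = 17) | 382.5 mg |
| 4 | 450 mg (n = 16) | 360 mg |

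For k = 1 to 4, the all-data mean runs from 285 to 240 mg if m = 300 mg, and from 570 to 480 mg if m = 600 mg.

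**5. Mean daily dose in the interval of the rescue itself.** SAP 4.10 divides by a fixed 28 days after Week 12. With 600 mg to Day 98, which is day 14 of the Day 85 to 112 interval, the result is 600 × 14/28 = 300 mg, whether or not the later 0 mg days are dropped. It becomes 600 × 14/14 = 600 mg only if the denominator is also cut at rescue, which the SAP does not say.

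**The case against.** The strongest reply is that a specific instruction normally overrides a general one. The windows in 7.5.2 and protocol 10.1.2 are specific, and SAP section 9 declares no shortening of them. A programmer may well follow them, and then nothing is lost. This stands: undercounting is certain only on the literal reading, and a flat claim that the rates are biased low goes further than the documents do.

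Some stronger inferences also fail:

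- A reader might infer that every second rescue goes uncounted. The whole-period endpoint counts subjects, so a repeat of the same type changes nothing there.
- A reader might infer that the drug stop required with an ESA rescue is always missed. The SAP exclusion starts the day after rescue, so a stop dated on the rescue day is kept.
- A reader might infer that later dose and iron summaries cover only never-rescued subjects. Subjects who are rescued later still contribute to every interval up to their rescue.

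Some of the information also appears outside the exclusion: interruptions by reason (7.2.2), and duration and cumulative dosage (7.4). This softens the loss but does not replace the tables. Section 7.2.2 tabulates cases of interruption by reason, with no proportion of subjects per interval. Section 7.4 gives no dose by interval. In the errata's list of output tables, the rescue proportions appear only as efficacy tables.

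Finally, dose and iron before any rescue could be a legitimate thing to describe. That is fair, but it is not what 7.5.2 asks for, and the tables would not be labelled that way.

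**Conclusion.** The point holds as an unreconciled conflict. SAP 6.3 and 7.5 and protocol 13.2(3) exclude post-rescue efficacy data without exemption, while the rescue, dose, adjustment and iron endpoints have windows to Week 24. The rule as written gives the wrong answer for these endpoints whenever a rescued subject stays in the study and has a later rescue of another type, or has dosing or iron data after the rescue day.

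The reach is limited. The tables concerned are for other endpoints. They are descriptive apart from the before-and-after tests on iron in 7.5.2(6) and (7). The Hb primary endpoints are not touched. The size cannot be stated, because no rescue rate is given and because ESA-rescued subjects who are not expected to resume study drug are withdrawn. The 5-point shift per subject assumes all 20 subjects are in the full analysis set. The dose figures rest on assumed dose levels and numbers stopped.

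**What to change.** In SAP 6.3 and 7.5:

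1. Limit the post-rescue exclusion to outcome measurements: Hb and the other laboratory values (lipids and glucose included), blood pressure, and QOL. Naming lipids, glucose and blood pressure matters because they are efficacy endpoints under 3.1.2(11), and a shorter list would lift the exclusion from them by accident.
2. State that the rescue proportions, study drug dosage, dose adjustments, and iron dose and use (7.5.2(3) to (7)) take all data to Week 24 or discontinuation, regardless of earlier rescue.
3. Record the departure from protocol 13.2(3) in SAP section 9. Protocol 13.4 asks for the reason in the SAP and in the study report.

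No new data are needed. Rescue details, study drug dose and iron dose are already recorded in the CRF (protocol 8.5.3, 9.2.2 and 9.2.3), and no clinical rule changes. The cost is a short SAP edit and its section 9 entry. The downside is that reported rescue and interruption rates may be slightly less favourable.

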### 7.5.1 Analysis of primary endpoint

(1) Mean Hb values at Week 20 and Week 24 of the treatment period

Descriptive statistics should be calculated for the primary efficacy endpoint of the mean Hb values at Week 20 and Week 24 of the treatment period. The MMRM is used to model the mean Hb values at each evaluation time point based on the following model, and the mean Hb values for Week 20 and Week 24 of the treatment period should be obtained, and the least squares mean (LSMean), its standard error, and 2-sided 95% CIs for the mean Hb values should be calculated.

[MMRM Model]

- Covariate: Response variable value of the first day of the treatment period
- Fixed effects: Evaluation time point
- Degrees of freedom adjustment: Kenward-Roger method
- Covariance matrix within subject for each subject: Unstructured (type = UN; unstructured)

If the variance-covariance matrix within subjects is not converged using unstructured data, the variance-covariance matrix within subjects should be changed in the following order, and the analysis should be performed using the variance-covariance matrix within subjects that converges first.

Heterogeneous Toeplitz (TOEPH) → Heterogeneous AR (1) (ARH [1]) → Heterogeneous CS (CSH) → Toeplitz (TOEP) → First-order autoregressive (AR [1]) → Compound symmetry (CS)

➤ Random effects: Subjects

(2) Hb values at each evaluation time point in the treatment period

Hb value and change of Hb from the first day of the treatment period at each evaluation time point of the treatment period should be obtained, and its descriptive statistics should be calculated. Before and after comparison will be conducted for changes of Hb from the first day of the treatment period to each evaluation time using the paired t-test.

LSMean, its standard errors, and 2-sided 95% CI of mean Hb values at each evaluation time point of the treatment period should be calculated using the MMRM model (with compound symmetry [CS] for a variance-covariance matrix within subjects) similar to that used in “mean Hb values at Week 20 and Week 24 of the treatment period”.

Furthermore, LSMean, its standard errors, and 2-sided 95% CI of the change from the first day of the treatment period should be calculated at each evaluation time point of the treatment period using the MMRM (with compound symmetry [CS] for a variance-covariance matrix within subjects).

The time course diagram should be prepared for mean Hb values at each evaluation time point in the treatment period. 95% CI of the mean will be represented by an error bar. The time course diagram should be prepared for Hb values at each evaluation time point of the treatment period in each subject.

(3) Proportion of subjects with mean Hb levels within the target range (10.0–12.0 g/dL), <10.0 g/dL, and ≥12.0 g/dL at each time point of the treatment period

The number, proportion, and 95% CI (Clopper-Pearson [Exact] method) of the proportion of subjects with Hb value within the target range (10.0 to <12.0 g/dL, within), <10.0 g/dL (below), and ≥12.0 g/dL (above) at each time point of the treatment period should be provided. Before and after comparison should be conducted for changes from the first day of the treatment period to each evaluation time point using the McNemar test.

The proportion of subjects in each Hb category (within the target range [10.0 to <12.0 g/dL], <10.0 g/dL, and ≥12.0 g/dL) at each evaluation time point of the treatment period should be provided as a stacked bar graph assuming that the number of subjects at each evaluation time point is 100%. Stacked bar charts should be separately prepared.

(4) Number of days from the first day of the treatment period required to reach the target Hb range (10.0 g/dL to <12.0 g/dL)

Descriptive statistics should be calculated for number of days required from the first day of the treatment period to reach target Hb range (10.0 g/dL to <12.0 g/dL). The number of days should be calculated as the first evaluation date reached target Hb range – first date of the treatment period

+ 1. If target Hb range is not reached, the final date of evaluations – first date of the treatment period + 1 should be assumed.

A Kaplan-Meier plot should be shown for days from the first day of the treatment period required to reach the target Hb range.

No subjects with an Hb value of  $\geq 10.0$  g/dL on the first day of the treatment period will be included in the calculation.

(5) Hb value increase rate

Descriptive statistics should be calculated for the Hb value increase rate (g/dL/week).

The Hb value increase rate should be analyzed by 2 methods defined in the “Hb value increase rate”.

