6.1 Target sample size

The number of subjects registered in the treatment period will be 20.

Rationale

The proportion of patients who are not treated with any ESA formulation is as small as approximately 10% of all hemodialysis-dependent patients in Japan. Patients receiving any ESA formulation are allowed to register after undergoing a washout; however, the number of eligible patients was thought to be very limited when considering the selection/exclusion criteria. Therefore, the target sample size was set to 20 after consideration of feasibility.

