13.3.2 Efficacy

(1) Analysis methods for primary endpoint

1) Mean Hb at treatment period Weeks 20 and 24

For mean Hb at treatment period Weeks 20 and 24, mean Hb at each timepoint will be modeled using MMRM with the following model, and mean Hb at treatment period Weeks 20 and 24 and their two-sided 95% CI will be calculated.

[MMRM model]

- Fixed effects: Evaluation timepoint
- Random effects: Subjects

2) Hb at each treatment period timepoint

Descriptive statistics will be calculated for Hb levels at each treatment period timepoint, and analysis performed taking into account changes over time using MMRM.

- 3) Proportion of subjects with mean Hb levels within the target range (10.0–12.0 g/dL), <10.0 g/dL, and ≥ 12.0 g/dL at each timepoint in the treatment period
Numbers and ratios of subjects with mean Hb at each treatment period timepoint within the target range (10.0–12.0 g/dL), <10.0 g/dL, and ≥ 12.0 g/dL will be shown.
- 4) Number of days from the first day of the treatment period required to reach the target Hb range (10.0–12.0 g/dL)
Descriptive statistics will be calculated for days from the first day of the treatment period required to reach the target Hb range (10.0–12.0 g/dL). A Kaplan-Meier plot will be shown for days from the first day of the treatment period required to reach the target Hb range (10.0–12.0 g/dL). Statistical summaries will not include subjects with Hb ≥ 10.0 g/dL on the first day of the treatment period.
- 5) Rate of increase in Hb levels
Descriptive statistics will be calculated for the rate of increase.

(2) Other endpoints

Incidence and ratios will be shown for discrete data, while descriptive statistics will be calculated for continuous data.

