### 2.2 Study design

Study phase: Phase III

Study type: Confirmatory study

Multicenter, uncontrolled, open-label study

Evaluation time point		Informed consent	Screening period [a]		Treatment period [b]											Final day of the follow-up observation [c]	
			First day	Visit 2	W2	W4	W6	W8	W10	W12	W16	W20	W24	Day of discontinuation			
Item	Visit	First day [b]	SV1	SV2	TV1	TV2	TV3	TV4	TV5	TV6	TV7	TV8	TV9	TV10	TV11	Final day of the follow-up observation [c]	
Permitted range (days)			-	-	-	-3	-3	-3	-3	-3	-3	-3	-3	-3	+7	or +14 [e]	
Procedure/evaluation																	
Informed consent		X															
Inclusion/exclusion criteria		X	X		X												
Patient background and history		X			X												
Height					X						X						
Dry weight, body weight [f]					X									X			
Folic acid and vitamin B 12 [g]					X										X		
Pregnancy tests [i]			X														
Hematology tests [g], [h], [i]		X	X [k]		X	X	X	X	X	X	X	X	X	X	X		
Blood biochemistry tests [g], [h], [i]		X			X	X	X	X	X	X	X	X	X	X	X		
C-reactive protein [g], [h]		X			X										X		
Iron-related measures [g], [h]		X			X	X	X	X	X	X	X	X	X	X	X		
Hepcidin [h]		X			X	X	X	X	X	X	X	X	X	X	X		
EPO [h]		X			X	X	X	X	X	X	X	X	X	X	X		
VEGF[h]		X			X										X		
Vital signs [g], [h], [m]		X			X	X	X	X	X	X	X	X	X	X	X		
Resting standard 12-lead ECG [h], [n]		X			X										X		
Fundoscopy [e]		X			X									X			
Chest X-ray [e]		X			X									X			
Duration of hemodialysis					X										X		
QOL measures (EQ-5D-5L, KDQOL)					X						X						
AE investigation					X	X	X	X	X	X	X	X	X	X	X		
Blood sampling for genetic analysis [o]																X	
Product evaluation/procedure																	
Investigation of concomitant medications/therapies					X	X	X	X	X	X	X	X	X	X	X	X	X
MT-6548 tablets [p], [q]																	
Iron supplements																	
Administered according to the dosage adjustment guidelines																	
Iron supplements administered to maintain serum ferritin values of $\geq 100$ ng/mL or TSAT of $\geq 20\%$																	

- [a] The screening period can be up to 6 weeks. Test results should be reviewed prior to transition from the first day of the screening period to screening period Visit 2 and from screening period Visit 2 to the first day of the treatment period. Re-testing can be performed as necessary.

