## 7. Statistical Method

### 7.1 Basic Matters

#### 7.1.1 Level of significance and confidence coefficient

When implementing tests, level of significance should be set at 2-sided 5%. Confidence interval (CI) will be 2-sided with a confidence coefficient of 95%.

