### 7.5.3 Adjustment for covariates

In the analysis of efficacy, in order to consider the effect of the measurement value of the first day of the treatment period on the change of each measurement, the analysis using the MMRM model (with compound symmetry [CS] for a variance-covariance matrix within subjects) should be conducted using the measurement value of the first day of the treatment period as a covariate in the general analysis including the analysis of the primary endpoint.

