## 9. Changes in the Statistical Analysis Plan from the Study Protocol

- (1) Mean corpuscular volume and mean corpuscular hemoglobin were added to the other efficacy endpoints.

Reason: Because the importance of mean corpuscular volume and mean corpuscular hemoglobin has increased in the efficacy evaluation from a clinical point of view.

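### The SAP adds a baseline covariate to the single-arm MMRMs without declaring it; the resulting intervals omit the sampling error of the baseline mean and are generally too narrow for mean change, and conditionally so for mean Hb

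*SAP*

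**What the plan says.** The trial is a "Multicenter, uncontrolled, open-label study" (SAP 2.2), and Protocol 6.1 sets 20 subjects on feasibility. Protocol 13.3.2 gives the MMRM for the Week 20/24 mean Hb as "Fixed effects: Evaluation timepoint" with subjects as a random effect, and names no covariate.

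SAP 7.5.1(1) keeps those two terms and adds "Covariate: Response variable value of the first day of the treatment period", with Kenward-Roger degrees of freedom and an unstructured matrix first. It asks for the LSMean, its standard error and its two-sided 95% CI. SAP 7.5.3 carries the adjustment into the efficacy MMRMs at large, "using the measurement value of the first day of the treatment period as a covariate". The MMRMs for change in Hb (7.5.1(2), 7.5.2(1)) use a compound-symmetry matrix.

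Protocol 13.4 requires that reasons for analysis changes made before data lock be described in the SAP. Section 9 of the SAP records one change only: "Mean corpuscular volume and mean corpuscular hemoglobin were added to the other efficacy endpoints". The errata do not mention the covariate either.

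**The concern.** In a randomised comparison the arms share a baseline mean, so its sampling error cancels from the contrast. Here there is no contrast: the reported quantity is the arm's own mean, or its mean change. An LSMean evaluated at the sample-average baseline answers what Hb would be for patients whose baseline equals this sample's average. Its standard error contains only the scatter left after regression on baseline. It has no term for the fact that another 20 patients would have a different average baseline, and Kenward-Roger does not supply one.

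Because the sample size was set on feasibility and there is no comparator, the estimate and its interval are the main efficacy output. Readers will take the interval as describing the patient population. If it is conditional on the observed baselines and does not say so, stated precision is usually better than the data support. The change from the protocol model also goes unrecorded where Protocol 13.4 says it should be recorded.

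**Working it through.** **Inputs from the documents.** n = 20 (Protocol 6.1); 95% two-sided intervals (SAP 7.1.1); the models quoted above. SAP section 8 names SAS 9.4 and no reference baseline is given, so evaluation at the sample-mean baseline is inferred from the software default. The documents give no SD or correlation and no precision target, so there is no plan figure to reproduce. The benchmark is the unadjusted t interval, which covered 94.8–95.3% in simulation at n = 20.

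**Assumptions.** σx = first-day SD, σy = Week 20/24 SD, ρ = their correlation, b = ρσy/σx = slope on baseline. All values below are assumed.

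**Closed form (complete data, slope the same at every visit).** The LSMean equals the raw visit mean.

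- Variance used by the model: σe²/n, with σe² = σy²(1 − ρ²).
- Sampling variance of mean Hb: (σe² + b²σx²)/n = σy²/n. SE ratio = √(1 − ρ²).
- Sampling variance of mean change: (σe² + (b − 1)²σx²)/n = SD(change)²/n. SE ratio = σe/SD(change), with SD(change)² = σx² + σy² − 2ρσxσy.

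The omitted term is zero for mean Hb only if b = 0, and for mean change only if b = 1. The adjusted SE is the same for both, so the two intervals cannot both be right unless baseline has no variance.

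**Worked case: σx = 0.65, σy = 0.9, ρ = 0.3.** b = 0.3 × 0.9/0.65 = 0.42. σe = 0.9 × √0.91 = 0.859. SD(change) = √(0.4225 + 0.81 − 0.351) = 0.939. SE ratios: mean Hb 0.954; mean change 0.859/0.939 = 0.914.

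| ρ | b | SE ratio, mean Hb | Coverage | SE ratio, mean change | Coverage |
|---|---|---|---|---|---|
| 0 | 0 | 1.000 | 95% | 0.9/1.110 = 0.811 | 89% |
| 0.1 | 0.14 | 0.995 | 94.9% | 0.848 | 90.8% |
| 0.3 | 0.42 | 0.954 | 94.0% | 0.914 | 92.9% |
| 0.5 | 0.69 | 0.866 | 91.4% | 0.969 | 94.3% |

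At ρ = 0.3 the half-widths are 0.40 g/dL adjusted against 0.42 unadjusted for mean Hb, and 0.40 against 0.43–0.44 for mean change.

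**Compound-symmetry mixed model, nine visits, simulated, constant slope.** For slopes 0, 0.3, 0.5 and 0.7, mean-change coverage was 86.3%, 90.5%, 92.7% and 94.2%; mean-Hb coverage was 94.9%, 94.0%, 93.0% and 90.8%.

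**Unstructured model, nine visits, simulated (SDs 0.6 and 0.9).** Mean change covered roughly 88–94% for slopes 0 to 0.75. With a constant slope, mean Hb covered about 93–94% at ρ = 0.3 and 90–91% at ρ = 0.5.

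**Declining slope.** SAP 7.5.1(1) has no baseline-by-visit term, so one slope is fitted to all visits. With the true slope falling from 0.8–0.9 at Week 2 to 0–0.3 at Week 24 (baseline SD 0.6, visit SD rising from 0.7 to 0.95), the unstructured model's SE for the Week 20/24 mean Hb was 3–13% wider than the unadjusted one, with coverage of 95–97%.

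**The case against.** The strongest reply is that the headline interval may not be too narrow at all. Baseline Hb is restricted (screening mean 8.0 to below 10.0 g/dL) and dose is titrated to a target range, so a weak correlation with Week 20/24 Hb is plausible. Below a correlation of about 0.09 the lost degree of freedom cancels the narrowing, and a slope that fades over visits can make the adjusted interval wider. This stands for mean Hb. It does not rescue mean change, for which a slope near zero is the worst case under a constant slope.

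Second, an interval conditional on the observed baselines is a standard covariance-adjusted quantity, and 7.5.3 states the adjustment and its purpose openly. That is fair, but the SAP does not tell the reader that the interval is conditional.

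Third, consequences are limited. No success threshold depends on these intervals, and unadjusted CIs and paired t-tests are also planned. The descriptive and MMRM results for the Week 20/24 mean Hb sit in separate tables (14.2.1.1.1 and 14.2.1.2.1), and the first uses LOCF. This holds, and it limits the point to stated precision.

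Fourth, the covariate can carry information about visits missing after discontinuation or rescue. This too stands, and simply deleting it loses that information.

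**Conclusion.** The point holds, with limits. The covariate is a departure from the protocol model that section 9 omits; that part needs no assumption. The LSMean intervals leave out the sampling error of the baseline mean, which follows from the model once the sample-mean reference is accepted.

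As population intervals they are generally too narrow for mean change unless the slope is near 1, and too narrow for mean Hb when the slope is non-zero and similar across visits. The sizes rest on assumed SDs, slopes and correlations.

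A reader might infer three stronger things that the documents do not support:

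- That the headline Week 20/24 mean Hb interval is certainly too narrow. It depends on a correlation and a slope pattern that the documents do not give. Coverage near 85% needs a correlation of 0.7, remote from an endpoint titrated to target.
- That every change-from-baseline MMRM is affected. With the slope near 1 the loss disappears.
- That the estimates themselves or the paired tests are compromised. With complete data the point estimates are unchanged, and the descriptive CIs and paired t-tests do not use the covariate.

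The SAP should be amended, because the plan reports these error bars as main results and a simpler model largely corrects them.

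**What to change.** 1. For the Hb level LSMeans (7.5.1(1) and (2)), remove the covariate and use the protocol model, with time point as the only fixed effect.
2. For change, report the unadjusted change. Alternatively, put the first-day value in the response vector as time 0 and estimate visit minus time 0, with an unstructured or heterogeneous covariance. Do not use compound symmetry for this: it pools the tighter differences between post-baseline visits, and in simulation coverage was 91–93% with a constant slope and 82–83% with a declining slope and rising SD.
3. Amend 7.5.3 to match, including its compound-symmetry instruction where the time-0 model is used.
4. If the covariate is kept, list it with a reason in section 9, state that the CI is conditional on the observed baselines, and add the baseline-mean variance: b²σx²/n for mean Hb, (b − 1)²σx²/n for mean change.

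The cost is SAP wording and usually slightly wider intervals. Dropping the covariate outright gives up some baseline information about missing visits; the time-0 model with an unstructured matrix keeps it. That matrix is large for 20 subjects, however: nine visits plus time 0 give 10 × 11/2 = 55 covariance parameters. A fallback that stays heterogeneous should therefore be named in advance. The unadjusted change is the simpler choice.
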